## 7. BACKGROUND AND SIGNIFICANCE

International health agencies [1] and chronic disease associations [2, 3] have called for reductions in free/added sugars to ≤5-10% of energy to address the growing epidemics of obesity and diabetes. Attention has focused especially on the reduction of the major source of free sugars, sugar sweetened beverages (SSBs), the excess consumption of which has been associated with weight gain, diabetes, and their downstream complications including hypertension, and coronary heart disease (CHD) [4-7]. Ontario's Healthy Kids Panel [8], Health Canada [9, 10], the Standing Senate Committee [11], the Heart and Stroke Foundation [2] and Diabetes Canada [3] have recommended policies to reduce SSBs including replacement strategies, taxation, and/or bans on advertising to children. A role for non-nutritive sweeteners (NNSs) in these policy options has been conspicuously absent.

There is an emerging concern that NNSs may contribute to an increase in the diseases that they are trying to prevent. Systematic reviews and meta-analyses of prospective cohort studies have shown that NNSs are associated with increased risk of weight gain, diabetes, and CHD [5, 12]. Although this evidence is recognized to be at high risk of reverse causality and disagrees with the higher quality evidence from randomized controlled trials [13], several biological mechanisms have been proposed, among them changes in gut microbiome. One highly-influential study [14] concluded that NNSs induce glucose intolerance through a loss of diversity in microbiome. This study, however, disagreed with a subsequent study [15] and had several methodological weaknesses including the lack of a control group. Despite the uncertainties, these data have contributed to a negative view of NNSs in the media [16-23].

There is an urgent need to address the ongoing concerns related to NNSs. Health Canada, in particular, has indicated that studies of sugar reduction strategies that use NNSs and target microbiome are an important research priority [24]. We propose to conduct a CIHR-funded randomized controlled trial that assesses the effect of a 'real world' strategy to reduce SSBs using non-nutritive sweetened beverages (NSBs) or water on gut microbiome, glucose tolerance, and cardiometabolic risk factors in overweight or obese participants.

## 8. OBJECTIVES

1. To assess the effect of replacing SSBs with NSBs or water on one primary outcome of diversity of gut microbiome over 4-weeks in overweight or obese participants.
2. To assess the effect of replacing SSBs with NSBs or water on another primary outcome of glucose tolerance over 4-weeks in overweight or obese participants.
3. To assess the effect of replacing SSBs with NSBs or water on the secondary and exploratory outcomes of body weight, blood pressure, glucose and insulin regulation, blood lipids, ectopic fat, liver fat, body adiposity, and diet quality over 4-weeks in overweight or obese participants

## 9. HYPOTHESIS

[figure not shown]
1. Replacing SSBs with NSBs or water will change the diversity of gut microbiome after four weeks in regular SSB drinkers.
2. Replacing SSBs with NSBs or water will increase glucose tolerance after four weeks in regular SSB drinkers.
3. Replacing SSBs with NSBs or water will decrease body weight, reduce blood pressure, improve glucose and insulin regulation, decrease blood lipids, decrease ectopic fat, decrease liver fat, decrease body adiposity, and improve diet quality after four weeks in regular SSB drinkers.

## 10. METHODS

**10.01 Trial Design.** We will conduct a single-centre, open label, randomized controlled crossover trial with three four-week intervention phases (SSB, NSB, water) comparing the effect of replacing SSBs with NSBs or water on the gut microbiome and glucose tolerance. A cross-over design was selected due to the high inter-individual heterogeneity in gut microbiome [25]. Prior to randomization, participants will undergo a ≥2-week run-in phase

to gather data on SSB consumption prior to study start. Each participant will then act as their own control receiving the 3 interventions in random order, each separated by a  $\geq 4$ -week wash-out phase (Figure 1). We will collect fecal samples from participants and conduct Oral Glucose Tolerance Tests (OGTTs) before the start and at the end of each intervention for gut microbiome analysis and glucose tolerance. All study visits will occur in Toronto at the Clinical Nutrition and Risk Factor Modification Centre at St. Michael's Hospital. The microbiome analysis and the objective biomarkers of SSBs assays will be performed at the Department of Nutritional Sciences, University of Toronto; plasma glucose analysis will be performed at the Banting and Best Diabetes Center (BBDC), University of Toronto; plasma insulin analysis and other blood analyses (for a selected sample using a multiplex kit for adiponectin, adiponisin, C-Peptide, Ghrelin, GIP, GLP-1, Glucagon, Insulin, leptin, PAI-1, Resistin and Visfatin) will be conducted at the Guelph Research and Development Centre, Ontario, Canada. Lipid analyses will be performed at St. Michael's Hospital Core Lab.

**Figure 1: Overview of the study visits and phase.\***

\*All possible groups are not shown.

**10.02 Blinding.** Blinding of the participants and investigators will not be possible due to packaging, taste and look of the interventions. However, outcome assessors (laboratory, microbiome analysis) and the statistician will be blinded to the identity of the treatments.

**10.03 Participants.** We will recruit 81 overweight or obese (ethnic specific cut-offs for overweight and obesity are used  $\geq 23$  kg/m^2 for Asian individuals and  $\geq 25$  kg/m^2 other individuals[11]), adult (age, 18-75 years) men and non-pregnant women (with no conception plans for the study duration) with a high waist circumference ( $\geq 94$ cm in men,  $\geq 80$ cm in women in Europid, Sub-Saharan African, Eastern Mediterranean, and Middle Eastern individuals;  $\geq 90$ cm in men and  $\geq 80$  cm in women for South Asian, Chinese, Japanese, and South and Central American individuals[26]) who are otherwise healthy (free of disease or illness), not taking medications that have a clinically relevant effect on the primary outcomes, not smoking, have no intentions of making major alterations to their diet or physical activity regime during study duration, and consuming  $\geq 1$  servings of SSBs per day (for which there is an NSB equivalent that contains the non-nutritive sweeteners acesulfame potassium or sucralose). Participants must be agreeable to consume only one type of SSB and brand-matched NSB for each month of intervention. If participants are consuming NSBs in addition to SSBs they must be willing to forgo them for the run-in and duration of the study. All participants must have a primary care physician and be proficient in English to be eligible for the study. Please see **Table 1** for a full set of exclusion criteria. SSBs will be defined as any sugar-sweetened beverage (sodas and soft drinks) that contains at least 50 kcal per 8-oz serving. For the purpose of the study, SSBs will NOT include fruit drinks, sports/energy drinks, sweetened iced tea, coffee, or homemade SSBs such as frescas or 100% fruit juice. All participants will be expected to participate in the study for approximately six months (one run-in phase of two weeks, three intervention phases of four weeks each, and two wash-out phases of four weeks each) and be able to attend all study visits. They must consent to have the

study drinks shipped to their home address by a third-party company, who will not be informed of their participation in the study, or be agreeable to pick up study drinks from the study site at St. Michael's Hospital.

Of the 81 participants, 30 of them will be asked to consent to have an MRI taken to measure their liver and muscle adiposity.

**Table 1 – Study exclusion criteria\***

Age <18 or >75 years
BMI <23 kg/m  for Asian individuals and <25 kg/m  other individuals
Waist circumference <94cm in men, <80cm in women in Europid, Sub-Saharan African, Eastern Mediterranean, and Middle Eastern individuals; <90cm in men and <80 cm in women for South Asian, Chinese, Japanese, and South and Central American individuals
Not regularly drinking SSBs ( $\geq 1$ serving per day)
Self-reported pregnant or breast feeding females, or women planning on becoming pregnant throughout study duration
Regular medication use that have a clinically relevant effect on the primary outcomes (except birth control and PRN meds such as Advil, Tylenol, etc)
Antibiotic use in the last 3 months
Complementary or alternative medicine (CAM) use as deemed inappropriate by investigators
Self-reported diabetes
Self-reported uncontrolled hypertension (or systolic blood pressure (BP) $\geq 160$ mmHg or diastolic BP $\geq 100$ mmHg [27])
Self-reported polycystic ovarian syndrome
Self-reported cardiovascular disease
Self-reported gastrointestinal disease
Previous bariatric surgery
Self-reported liver disease
Self-reported uncontrolled hyperthyroidism or hypothyroidism
Self-reported kidney disease
Self-reported chronic infection
Self-reported lung disease
Self-reported cancer/malignancy
Self-reported schizophrenia spectrum and other psychotic disorders, bipolar and related disorders, and dissociative disorders
Major surgery in the last 6 months
Other major illness or health-related incidence within the last 6 months
Smoker
Regular recreational drug users
Heavy alcohol use ( $>3$ drinks/day)
Do not have a primary care physician
Participation in any trials within the last 6 months or for the duration of this study
Any condition or circumstance which would prevent you from having an MRI (e.g. having prostheses or metal implants, tattoos, or claustrophobia) (this is applicable for the 30 participants in the MRI portion of the study)
Individuals planning on making dietary or physical activity changes throughout study duration

\*Disease exclusions will be based upon self-reported diagnosis

#### **10.04 Sample Size (Power) Calculation.**

The study will be performed in a total of 81 participants. It is powered to show a difference between the water, NSB, and SSB arms in 60 participants in the two primary outcomes. Assuming a drop-out rate of 20 percent, we

would need 75 participants in order to have the power to detect a difference. Since our final recruitment strategy resulted in a large number of participants who made it through the run-in phase, we decided to increase our recruitment in order to replace drop outs and thus will recruit 81 participants.

One primary outcome is in beta diversity of the gut microbiome communities of the participants between water and NSB groups via 16S ribosomal rRNA gene sequencing. We used the micropower R package to compute sample size based upon the power of 16S tag sequencing that can be analyzed using pairwise weighted UniFrac distances [28]. UniFrac is a distance metric based upon the unique fraction of branch length in a phylogenetic tree built from two sets of taxa. Comparison of microbiome samples is performed via weighted UniFrac, which considers the relative abundance of taxa. We simulated the within-group distance as 0.2, and the standard deviation (SD) of within-group distances as 0.07. To detect a weighted UniFrac distance of 0.04, which is smaller than the effect observed in a study of Suez et al. [29] (0.05 derived from figure 5), and considering it is a cross-over study with a within-person correlation of 0.7, and taking into account multiple arms we calculated that for above 95 percent power we would need 60 participants in this study. Assuming a loss of 20 percent, we will recruit 75 participants. We are confident about detecting an alteration in gut microbiome diversity if it exists as previous studies show that small changes in diet causes significant alteration in gut microbiome taxa over a much shorter period (5 to 7 days) in fewer individuals (10 to 25 people) [25, 30].

Another primary outcome is glucose tolerance, as measured by incremental Area Under the Curve (iAUC) from a 2-hour 75g OGTT. With 60 participants we will have 89 percent power (assuming absolute numbers for mean and SD from our recent unpublished randomized trial) to detect a 20% change in mean iAUC between the water and NSB group if the direction of change is similar to Suez et al. [29] while assuming a within-person correlation of 0.7 and taking into account the three comparisons. The 20% difference for glucose iAUC is based on the minimally important difference proposed by Health Canada to support postprandial blood glucose response reduction claims [31].

This power calculation takes into account adjustment for multiple testing for both primary outcomes using the Benjamini-Hochberg procedure, which is a suggested method by the Food and Drug Administration in its “Multiple Endpoints in Clinical Trials Guidance for Industry” [32]. Benjamini-Hochberg procedure is a step-down method that controls for false discovery rate, while maintaining high power [33, 34]. We will implement a truncated Benjamini-Hochberg method with parallel gatekeeping in which some portion of the unused alpha from each step is reserved for passing to the secondary outcome family if any of the primary outcome is significant. The alpha levels calculated for the primary outcomes is given in table 2. The study is also powered to show a difference between the three arms for secondary outcomes with an  $\alpha=0.0125$ , the lowest possible starting  $\alpha$  for secondary outcomes based upon the truncated Benjamini-Hochberg procedure.

Sub-study: 1H-MRS will be performed in 25 subjects to assess intrahepatic and intramuscular fat. We will have 99% to show a difference in liver fat of 5% between the water and NSB arm for both hepatic and muscle fat assuming a between group SD of 4%, with a correlation of 0.65 and alpha of 0.05.

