**Table 2. Power calculation for primary outcomes between water and NSB arms**

Outcome type	Outcome	Mean change	SD	Correlation	N	Alpha*	Power (Beta)	N (corrected for 20% loss to follow up)
Primary outcomes family								

Primary	Microbiome UniFrac Distance	0.04	0.07	0.7	60	0.0375	98%	75
Primary	Glucose iAUC	44.81 mmol/L/min (20%)	113 mmol/L/min	0.7	60	0.025	89%	75

P-value order will be from largest to smallest.

**10.05 Recruitment.** Participants will be recruited through postings and flyer handouts at St. Michael's Hospital, the University of Toronto, local clinics, and surrounding areas, advertisements in newspapers and on transit, and online listings on Craigslist and Kijiji. Some participants will complete a Survey Monkey to assess general eligibility. We will be utilizing a digital marketing group, TrialFacts, to launch a campaign to recruit participants. TrialFacts works exclusively with research groups to provide specialized patient recruitment services for clinical trials. Participants will be screened first by telephone. Eligible participants will be called in for an information session on the study including being provided the consent form. Those that wish to participate will provide written consent and will subsequently have an in-person screening including blood work. Based on our most recent FACE trial (NCT02459834), we estimate a recruitment rate of 1-2 participants/week and therefore plan to recruit all the participants within a 6-month period. **[name]** will organize the recruitment. Our **MSc candidate #1 ([name], RD)** and our **Research Coordinator** will conduct the screening.

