### **11. Statistical Analysis**

Data will be analyzed according to an intention to treat (ITT) principle using mixed models in STATA 14 (StataCorp, Texas, USA). Sensitivity analysis will be performed on the basis of complete data availability for primary endpoints. A separate sensitivity analysis will be performed on the basis of antibiotic use during the trial.

**Primary outcomes.** Repeated measures mixed effect models will be used to assess changes in the two primary outcomes i) beta diversity and ii) glucose iAUC between the groups. Pairwise comparisons between interventions will be performed using Tukey-Kramer adjustment or other appropriate statistics. For all primary outcomes effect modification by sex will be explored. We will use the truncated Benjamini-Hochberg false discovery rate controlling method with parallel gatekeeping procedure to correct for multiple comparisons for all primary outcomes [32].

**Secondary outcomes.** Repeated measures mixed effect models be used to assess changes in weight, waist circumference, fasting glucose, 2hr plasma glucose, and MATSUDA. Pairwise comparisons between interventions will be performed using Tukey-Kramer adjustment or other appropriate statistics. For all secondary outcomes

effect modification by sex will be explored. We will use the truncated Benjamini-Hochberg false discovery rate controlling method with parallel gatekeeping procedure to correct for multiple comparisons for all secondary outcome comparisons [33] if at least one primary outcome reaches significance. If none of the primary outcomes reach significance, the secondary outcomes will be analyzed as exploratory variables with no adjustment for false discovery rate.

**Exploratory and adherence outcomes.** Repeated measures mixed effect models will be used to assess changes in all exploratory outcomes without controlling for false discovery rate. Pairwise comparisons between interventions will be performed using Tukey-Kramer adjustment or other appropriate statistics. Effect modification by sex will be explored.

**Subgroup Analysis.** A priori analysis will be conducted by age, sex, ethnicity, baseline BMI, baseline WC, baseline FPG, baseline 2hPG (OGTT), baseline iAUC, medication use, sweetener blend (intervention), beverage type (intervention), and background sweetener use.

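### Secondary power is claimed at the family alpha of 0.0125 rather than at a level any single outcome faces; truncation in the last family gives up power; and Section 11 does not say which contrast opens the gate

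*Combined protocol and SAP*

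**What the plan says.** **The gate.** Section 10.04 describes truncated BH with parallel gatekeeping, in which alpha is "reserved for passing to the secondary outcome family if any of the primary outcome is significant". Section 11 repeats the condition. If at least one primary is significant, the five secondaries get the truncated false-discovery-rate (FDR) correction; otherwise they are exploratory, without it.

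**The secondary power claim.** Section 10.04: "The study is also powered to show a difference between the three arms for secondary outcomes with an" alpha of 0.0125, described as the lowest level at which the secondaries could start. No secondary effect size, SD or power value is printed.

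**Which contrast counts.**
- Section 9 sets SSB against its two replacements: "Replacing SSBs with NSBs or water will increase glucose tolerance after four weeks in regular SSB drinkers".
- Section 10.04 opens with all three arms: "It is powered to show a difference between the water, NSB, and SSB arms in 60 participants". It then describes the beta-diversity outcome as a water vs NSB comparison.
- The power table is titled "Power calculation for primary outcomes between water and NSB arms", although the glucose power statement allows for three comparisons.
- Section 11 tests every pair: "Pairwise comparisons between interventions will be performed using Tukey-Kramer adjustment or other appropriate statistics".

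**Direction of testing.** Section 10.04: "Benjamini-Hochberg procedure is a step-down method that controls for false discovery rate, while maintaining high power". The note under the power table: "P-value order will be from largest to smallest".

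**The concern.** Three parts of the multiplicity plan do not fit together.

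First, a power statement should use a level at which an outcome can be declared significant. A level shared by five outcomes is not that, unless the outcome has the largest of the five p-values under ordinary BH and all five pass. The power table does this properly for glucose, using the smaller primary threshold (0.025); the secondary sentence does not.

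Second, truncation holds back alpha so that a later family can be tested. No family follows the secondaries, because exploratory outcomes are analysed without FDR control. What is held back is simply lost.

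Third, the gate is a yes/no event that fixes the inferential status of five outcomes, yet each primary has three contrasts and Section 11 does not say whose p-value decides. Section 12 asks whether NSBs resemble water, while Section 9 expects replacement of SSBs to help. If both are true, the contrast in the power table is null, and the plausible readings of the gate then diverge most. Left open, the choice could be made after the results are seen.

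**Working it through.** **Inputs.** From Section 10.04 and its power table: n = 60, glucose iAUC difference 44.81, SD 113, within-person correlation 0.7, primary alphas 0.0375 and 0.025, stated glucose power 89%. Section 10.11 lists five secondaries. Two-sided tests are assumed.

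**1. The plan's own power figure.** SD of a paired difference = 113 × √(2 × (1 − 0.7)) = 113 × √0.6 = 87.5. Standardised difference = 44.81 / 87.5 = 0.512. A paired t test with 60 participants gives 94.9% at 0.025 and 88.7% at 0.025/3. The stated 89% therefore already pays for three comparisons.

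**2. The truncation fraction.** The truncated BH threshold for rank i of m is α × [γ × i/m + (1 − γ)/m]. With α = 0.05, m = 2 and γ = 0.5:
- rank 1: 0.05 × (0.25 + 0.25) = 0.025
- rank 2: 0.05 × (0.50 + 0.25) = 0.0375
- passed on after one success: 0.05 − 0.0375 = 0.0125

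All three match the document, so γ = 0.5 is implied, though not stated.

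**3. Secondary thresholds with 0.0125 passed on, m = 5.**

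| Rank | 1 | 2 | 3 | 4 | 5 |
|---|---|---|---|---|---|
| Truncated, γ = 0.5 | 0.0025 | 0.00375 | 0.005 | 0.00625 | 0.0075 |
| Ordinary BH | 0.0025 | 0.005 | 0.0075 | 0.01 | 0.0125 |

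Under the specified procedure no rank reaches 0.0125. If both primaries succeed and 0.05 is passed on, the strictest step is 0.05/5 = 0.01.

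**4. What the level means for power** (paired t, n = 60; the baselines are assumptions).
- Standardised difference 0.443: 80% at 0.0125, about 78% at 0.01, 61% at 0.0025, and 47% at 0.0025/3 if three contrasts are also charged.
- Standardised difference 0.501: 90% at 0.0125, 76% at 0.0025.

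**5. Truncated against ordinary BH in the last family.** Simulated power per responding outcome, 0.0125 passed on, the 80% case, independent outcomes:

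| Responders | Ordinary | Truncated |
|---|---|---|
| One | 61.1% | 61.0% |
| Two | 66.9% | 64.2% |
| Five | 77.6% | 71.7% |

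At correlation 0.5 the five-responder figures are 76.0% and 70.5%. The highest simulated FDR, over zero to four real secondary effects and correlations 0 and 0.5, was 4.92% (ordinary) and 4.85% (truncated).

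**6. The gate.** Three-arm crossover, 60 completers, 118 error df, no UniFrac effect, independent primaries. The gate opens if the larger primary p ≤ 0.0375 or the smaller ≤ 0.025.

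| Glucose scenario | Water–NSB, unadjusted | Water–NSB, Tukey | Any Tukey contrast |
|---|---|---|---|
| No differences | 4.9% | 1.9% | 5.0% |
| Only SSB differs, by 44.81 | 4.9% | 1.8% | 97.0% |
| Only SSB differs, by half that | 4.9% | 1.9% | 40.7% |
| SSB > NSB > water, equal steps, 44.81 in all | 40.6% | 26.6% | 91.5% |
| NSB differs from both by 44.81 | 95.5% | 90.5% | 97.0% |

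An omnibus F test opens the gate in 97.5% of trials in the second row. The smallest unadjusted p-value opens it in about 12.5% of trials with no differences at all.

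**7. Cost of a Tukey gate to glucose.** Tukey at 0.025 equals an unadjusted per-contrast level of 0.0093; water vs NSB power is 90.4%, against 94.9% for that contrast alone at 0.025.

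**The case against.** Powering on one contrast and testing all three are compatible. The glucose power allows for three comparisons and Section 11 names Tukey-Kramer, so three adjusted contrasts is a fair reading; the beta-diversity description in Section 10.04 points instead to water vs NSB. This stands: the documents are not flatly contradictory. They support two readings, and Section 11 carries neither into the gate.

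A reader might take the 97% as the expected size of the problem. The documents do not support that. They give no SSB effect, and 97% assumes the full powered glucose difference; at half it is 41%, at a quarter 12%. When NSB differs from both other arms, the case nearest to the powered one, the readings largely agree (91–97%).

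A reader might infer that a closed gate leaves the secondaries untested or wholly unadjusted. It does not: they are still analysed, with Tukey-Kramer across pairs. Only the FDR step and the confirmatory status go.

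A reader might also conclude that 60 completers are too few for the secondaries. That cannot be shown without secondary effect sizes and SDs; an outcome with 99% power at 0.0125 still has 96% at 0.0025. The 0.0025 step binds only when one primary succeeds and no other secondary helps, whereas Section 9 expects broad improvement. Under ordinary BH, 0.0125 is also a genuine threshold for the largest p-value. All this limits the size of the point, but the sentence still names a level that the specified procedure does not apply to any single outcome when 0.0125 is what is passed on.

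**Conclusion.** The point holds in three limited parts.

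1. The secondary power claim uses a family-level alpha. With one primary significant, single-outcome thresholds are 0.0025 to 0.0075 as specified, or 0.0025 to 0.0125 under ordinary BH. The loss ranges from about 2 points (80% to 78%, both primaries significant) to 19 points (80% to 61%, one primary significant and a lone responder). The 80% is an assumed baseline, and the claimed power itself cannot be checked.
2. Truncation in the last family costs up to about 6 points (72% against 78% with five responders) and protects nothing downstream.
3. The gate p-value is not defined. If water and NSB are alike and only SSB differs, with UniFrac null, the gate opens in 2–5% of trials on water vs NSB and in 41% to 97% on any Tukey-adjusted contrast, for an SSB glucose effect between half and all of the powered difference. These figures assume 60 completers, correlation 0.7 and γ = 0.5.

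The primary estimates and primary thresholds are unaffected. What is at stake is the inferential status of the five secondaries and the accuracy of one power sentence, which should be settled before unblinding. The step-down label is wrong for a procedure that starts from the largest p-value, but it changes at most about 0.4% of trials in the independent cases simulated.

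**What to change.** - **Secondary power sentence (Section 10.04).** Restate it at the 0.0025 step, printing effect size, SD, contrast adjustment and power for each outcome, or delete it.
- **Secondary family (Section 11).** Use ordinary BH at the passed alpha. State the truncation fraction for the primaries, the alpha passed after one and after two successes, and that the secondary family is five p-values, one per outcome.
- **Gate (Section 11).** Name one multiplicity-adjusted p-value per primary. The options are the smallest Tukey-Kramer adjusted p (which fits the three comparisons already charged in the 89%), an omnibus test, or water vs NSB alone. The choice is the sponsor's; the hypotheses and the power table should then be aligned with it. Remove the open-ended alternative to Tukey-Kramer for this test, and rule out the smallest unadjusted p.
- **UniFrac.** Say how pairwise between-sample distances become the p-value that enters the gate.
- **Wording.** Change step-down to step-up.

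**Cost.** SAP text and one recalculation; no change to sample size, visits or primary thresholds. Choosing the Tukey rule over water vs NSB alone gives up at most 4.5 points of glucose power on that contrast (94.9% to 90.4%), which is still not below the stated 89%. Choosing water vs NSB alone means accepting that the gate stays closed in about 95% of trials when the two are alike.
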